3 OBJECTIVES

The primary objective is to compare the maximum flexion, both passive and active at every clinical follow-up time point up till 5 years postoperative, measured with a large goniometer. Our primary hypothesis is that the Scorpio NRG PS knee prosthesis has an average flexion of at least 7 degrees higher than the Scorpio PS knee prosthesis. Secondary objectives are to assess the complications, Chair raise test outcomes, knee pain (VAS) and surgery time. The secondary hypothesis is that there is no difference in complications and pain during the stair climb and chair raise test between the Scorpio NRG PS and the Scorpio PS. So more flexion does not result in more anterior knee pain. Also, the validity of computer navigated measurements and the relation between patella tilting and post-operative pain will be evaluated.

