4 METHODS

Performance will be clinically measured using the Knee Society Score (Ewald, 1989; appendix 2). As part of the KSS flexion will be measured, both passive and active. The measurement will be done by a physiotherapist. Like the patient the physiotherapist will be blinded for the treatment.

The Chair Raise test(standing up from a firm straight-backed chair keeping the arms folded across the chest) and stair climb test(ascending a flight of eleven 17.8 cm tall steps with an 30 cm tread depth, use of one hand rail is allowed) is combined with a 10 point VAS measurement of anterior knee pain(McCormack et al., 1988). This consists of a pain scale from 0 to 10 on which the patient can point to the amount of pain (0 means no pain, 10 means the worst possible pain) Recording of the nature and incidence of all intra-operative and post-operative complications will be the method to assess safety. The difference between computer navigation measurements of leg axis and range of motion and clinical and X-ray measurements of these parameters will be evaluated. For this evaluation the pre-op standard X-rays and the per-operative computer navigation data will be used.

The relation between patella tilting and post-operative pain will be measured during functional tests Stair climb and chair raise according to a Visual analog scale (VAS) .

Patellar tilting will also be assessed on consecutive X-rays by the orthopaedic surgeon.

A WOMAC patient questionnaire (appendix 3) will be done to evaluate the patient's opinion on recovery, post-operative pain, and function(Bellamy et al., 1988).

An EQ-5D patient questionnaire (appendix 3) will be done to evaluate the patient's opinion of their health status (mobility, self-care, usual activities, pain/discomfort, anxiety/depression and a visual analog scale (VAS) to measure the patient's self-rated health outcome).

All evaluations will be conducted on the follow up moments mentioned in the follow up table

at page 8.

The prostheses used in this study both have a CE mark. All information concerning these prostheses is attached as appendix 4

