6 SELECTION OF PATIENTS

6.1 *Number of patients*

The number of patients is based on average postoperative flexion as the primary endpoint. According to Morawa¹⁰ Scorpio patients showed a maximum post-operative flexion of 104 degrees. An increase in maximum flexion of 5 degrees is already noticeable for the patient, so clinically important. According to pre marketing results the Scorpio NRG PS knee prosthesis can reach a flexion of more than ten degrees extra compared to the Scorpio PS. For the primary endpoint we want to aim at an increase in maximum flexion of 7 degrees. According to Schouten¹² a sample size of 40 patients in each group is needed with a difference in flexion of 7 degrees, a standard deviation of 11^{7,8} a 80% power with a significance level (alpha) of 0.05 (two-tailed). When we take into account a lost of FU of 10% a total groupsize of 88 is anticipated.

6.2 *Patient selection criteria*

All patients on the waiting list for a total knee prosthesis at the department of orthopaedics at the AZM will be checked for suitability for this study. Patients will be verbally and in writing informed about the study during the first visit related to the TKP, and will be provided with the patient information. One week before surgery during a pre-operative visit the patients will be orally informed again, All questions about the study will be answered and the patient will be asked to participate in this study. If a completely informed patient wants to participate, the informed consent will be signed.

If a patient doesn't want to participate it is very likely that he will receive the Scorpio PS prosthesis since this is the standard used knee prosthesis at the AZM. If a patient does or doesn't want to participate has no effect on day of surgery or further medical care.

The confidentiality of the subject will be maintained at all times. The patient will be told that he/she is free to refuse the collection of his/her clinical data or to withdraw from the Investigation at any time without compromising future medical care.

TABLE 1. Patient Inclusion and Exclusion Criteria

Inclusions

- Patients requiring a primary TKA
- Male and nonpregnant female patients
- Between 18 and 80 years of age at time of surgery
- Patients with a diagnosis of osteoarthritis (OA), avascular necrosis (AVN), and not severe posttraumatic arthritis
- No previous osteosynthesis of the involved knee during the last 12 months

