9.1.4 Post-operative Evaluation

Patients will be assessed at post operative intervals at 6 weeks 3 months, 6 months 1, 2 and 5 years.

Post-operatively

- **Clinical Evaluation(*physiotherapist*)**
 - Date of assessment
 - Complications
 - Knee Society Score Evaluation
 - Pain
 - Walking
 - Stairs
 - Support
 - Flexion Contracture
 - Extension Lag
 - Range of Motion (active and passive)
 - Stability-anterposterior
 - Mediolateral stability
 - Patella tracking
 - Chair raise test, stair climb test
 - WOMAC, EQ-5D patient evaluation questionnaires

- **Radiographic Evaluation(*clinical researcher*)**

- Date of graphs taken
- AP and Lateral view
- Radiolucencies
- Patella tilt

9.2 *Adverse event/ Complications (surgeon)*

- Intra-operative and post-operative complications
- Date of event/complication
- Local complications
- Mechanical complications
- Revision required
- General complications
- Outcome complication

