14.1 Statistical Analysis

There will be summaries and comparisons presented according to:

- Demographic and pre-operative assessments
- Operative assessments
- Post-operative pain and function assessments
- Chair raise and stair climb assessment
- Patella-tracking assessment
- Adverse events
- General complications
- Local complications
- Device-related complications
- Revisions/removals

Descriptive statistics will be used like frequency and percent distributions and will be presented in tabular form for categorical variables. The mean, standard deviation, minimum and maximum values will be presented for quantitative variables. Students T-test will be used to compare variables between groups and various time points.

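### The primary objective spans 12 flexion comparisons, the trial is sized for one, and the plan never says which one decides

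*Combined protocol and SAP*

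**What the plan says.** Section 3 (Objectives) makes it the primary objective to "compare the maximum flexion, both passive and active at every clinical follow-up time point up till 5 years postoperative". The primary hypothesis that follows is a single statement: "the Scorpio NRG PS knee prosthesis has an average flexion of at least 7 degrees higher than the Scorpio PS knee prosthesis". It names no visit and does not choose between active and passive flexion.

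Section 4 (Methods) confirms two measures per visit: "As part of the KSS flexion will be measured, both passive and active". Section 9.1.4 lists the visits: "Patients will be assessed at post operative intervals at 6 weeks 3 months, 6 months 1, 2 and 5 years". Table 2 ticks the clinical and KSS evaluation at the same six post-operative visits and not at discharge.

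Section 6.1 states: "The number of patients is based on average postoperative flexion as the primary endpoint". The calculation uses a difference of 7 degrees, an SD of 11, 80% power and a "significance level (alpha) of 0.05 (two-tailed"), and arrives at 40 per group and 88 in total. Neither the SD nor the 10% loss is tied to a visit or a measure.

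On inference, Section 14.1 says only: "Students T-test will be used to compare variables between groups and various time points".

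**The concern.** Two measures at six visits make 12 primary comparisons, but the sample size and the alpha belong to one. Nothing in the plan connects the two. There is no primary visit, no primary measure, no per-patient summary or repeated-measures model across visits, and no multiplicity rule.

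This matters on either reading:

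- **One comparison decides.** The 5% error rate would hold, but the plan does not say which comparison it is. The result presented as the trial's answer could be picked from 12 once the data are known. Section 15 plans a two-year paper and a separate five-year paper and does not say which one answers the primary hypothesis.
- **Each comparison is tested at 0.05**, the only alpha the plan gives. If any significant result is then taken as support for the hypothesis, the chance of a false claim is well above 5%.

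**Working it through.** **Inputs from the documents.** Difference 7 degrees, SD 11, two-sided alpha 0.05, power 80%, 40 per group, 10% loss, 88 in total (Section 6.1); two measures (Sections 3 and 4); six visits (Table 2, Section 9.1.4).

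**1. The plan's own figure.** Normal approximation: n per group = 2 × [11 × (1.960 + 0.842) / 7]² = 38.8, so 39. The t-based calculation gives 39.7, so 40. With 40 per group the noncentrality is (7/11) × √(40/2) = 2.846 and the critical value is t(78) = 1.991, which gives power 80.3%. The stated 40 is therefore the size for exactly one t-test at 0.05. The total is 80 × 1.10 = 88.

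**2. Number of comparisons.** 6 visits × 2 measures = 12.

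**3. Chance of at least one false positive among 12 tests at 0.05.** With independent tests it is 1 − 0.95¹² = 46.0%. This is only an upper reference, because the measurements come from the same knees and are correlated. The documents give no correlations, so the following are assumptions. I simulated 400,000 draws of 12 correlated z-statistics with no true difference. The correlation between two statistics was the between-visit value times the active-passive value, with active-passive set to 0.9.

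| Between-visit correlation | Any of 12, either direction | Any of 12, favouring the new design | One measure, six visits, either direction |
|---|---|---|---|
| Equal, 0.5 | 27.7% | 13.9% | 20.7% |
| Equal, 0.8 | 18.8% | 9.4% | 13.9% |
| Decaying (AR(1)), 0.5 | 31.5% | 16.2% | 23.4% |
| Decaying (AR(1)), 0.8 | 23.1% | 11.6% | 17.1% |

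The nominal values are 5% in either direction and 2.5% favouring the new design. Over a wider grid (between-visit 0.3 to 0.9, active-passive 0.8 to 0.95) the either-direction figure runs from 13.6% to 37.1%. The last column shows that choosing between active and passive alone would not solve the problem.

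**4. Adjusting for all 12.** The Bonferroni level is 0.05/12 = 0.00417. With 40 per group the noncentrality is still 2.846, but the critical value rises to 2.952, and power per test falls to 46.3%. Restoring 80% per test needs 70 analysed per group (t-based).

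**5. Requiring all 12 to be significant.** This would not inflate the error rate, but it costs power. With 40 per group and a true 7-degree difference throughout, power is about 37% to 63% (equal between-visit correlation 0.5 to 0.9, active-passive 0.8 to 0.95).

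**The case against.** The strongest reply is that the plan does have one endpoint and one hypothesis. Section 6.1 speaks of a single primary endpoint, the hypothesis in Section 3 is one 7-degree difference, and the Study Design Summary also refers to average motion. On that view the objective merely lists when flexion will be compared. No section says that any one significant result out of 12 counts as success, so the inflated error rate depends on a rule the plan does not state, and on assumed correlations.

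Part of this stands. The error rates are conditional illustrations, and the 46% figure should not be quoted as the actual rate. Because the hypothesis is directional, the 9% to 16% range is the more relevant one for a false claim in favour of the new design. The single-endpoint reading does not remove the defect, however. *Average* is never defined as an average over visits or over the two measures, and it can equally mean the group mean at each visit. The SD of 11 is not described as that of a multi-visit average. The sentence before the hypothesis asks for both measures at every visit. A singular endpoint that cannot be identified leaves the choice open.

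Two smaller points change nothing material. Active motion is also recorded at discharge (Section 9.1.3), which would make 13 comparisons, but Table 2 has no clinical and KSS evaluation there. And 88 patients less 10% leave 79.2, or 39.6 per group, with power 79.9% rather than 80.3%. Blinding of the patient and the physiotherapist limits measurement bias, but it does not prevent selection of the result afterwards.

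**Conclusion.** The concern holds and must be fixed, because it governs the trial's main conclusion. That the primary comparison is unidentified follows from the text alone and needs no assumption. The size of the error inflation does rest on assumptions: that each of the 12 comparisons is tested at 0.05, that any one significant result counts, and that the correlations are as assumed. Under those, the false-positive chance is about four to six times the stated 5% (18.8/5 = 3.8; 31.5/5 = 6.3). Even the most favourable case on the wider grid, 13.6%, is nearly three times 5%. The sample size arithmetic itself is sound for one comparison.

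**What to change.** Before any data are seen by group, name one primary comparison and use the same definition in Sections 3, 6.1 and 14.1 and in the Study Design Summary. It can be one measure (active or passive) at one visit, or one defined per-patient summary across visits; the choice is the sponsor's. Test it once, two-sided, at 0.05. Report the other measure and the other visits as secondary estimates with 95% confidence intervals.

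**Cost.** For one measure at one visit this is a change of wording: 40 per group keeps 80.3% power, with no extra patients or visits. Section 6.1 should then say that the SD of 11 and the 10% loss apply at that visit. A summary across visits would have its own SD, so its power would have to be stated. Significance claims at other visits become secondary.

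If formal claims at several visits are wanted, prespecify a procedure such as Holm across the 12 tests and state its power. That is not free. At the Bonferroni level, a lower bound for Holm, power per test with 40 per group is about 46%. Guaranteeing 80% per test needs about 70 analysed per group, which with 10% loss is 140/0.9 = 155.6, so 156 enrolled instead of 88.

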2 STUDY DESIGN

This is a prospective single-centre post market randomized comparative study.

2.1 *Pre-operative inclusion*

Patients on the waiting list for a total knee prosthesis who fulfil the inclusion and exclusion criteria will be asked to participate in this study. Oral and written information (appendix 1)

about the study will be given to the patient at the first hospital visit, related to the TKP. Oral information will be given again at a pre-operative information meeting one week before surgery. All study information will be given by the scientific researcher and orthopaedic surgeon. When a patient wants to participate the informed consent (appendix 1) will be signed and all pre-operative study information will be completed. This consists of demographics, medical history, a knee society score evaluation (KSS) (appendix 2), a stair climb and chair raise test combined with a VAS (visual analogue scale, appendix 3) score to measure pain. The VAS score is a 10 point scale with zero as no pain and 10 as the worst possible pain. A WOMAC patient questionnaire (appendix 3) and EQ-5D patient questionnaire on health status (appendix 3) will be done and additional X-rays will be made to measure pre-operative patella tracking and tilting.

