9 PATIENT EVALUATIONS

Patients will be assessed pre-operatively, per-operatively and post-operatively. Appropriate data will be recorded both in their hospital notes and case report forms. The follow-up intervals are described in the following table.

Table 2: follow up intervals

Evaluation	Pre-op	Per-op	Post-operatively						
			Prior to Discharge	6 wks	12 wks	26 wks	1 Year	2 Years	5 Years
Medical History	√								
Clinical + KSS	√			√	√	√	√	√	√
Operative Data		√							
Chair Raise test Stair climb test	√			√	√	√	√	√	√
X-rays A/P en lateral	√		√	√	√	√	√	√	√
X-rays Long leg	√				√				
X-rays Patella defile	√				√	√	√	√	√
WOMAC, EQ-5D Patient evaluation	√				√	√	√	√	√

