15 PUBLICATION OF RESULTS

For this study, as a single-centre Stryker Initiated Study, the following shall apply:

Ownership of data

- Study data owned, managed and analysed by Stryker SA

Publication plan

- Collectively defined and agreed by Stryker and Principle Investigator before study start
- Analysis timelines
- Covers Journals, Congresses and according timelines
- **2 year after completion of follow-up we plan to submit an abstract with preliminary findings to ORS and EFORT and the National Dutch Orthopaedic Association meeting.**
- **We plan to submit a two year data paper to either JBJS Br or Acta Orthopaedica depending on the data outcome and its relevance to the orthopaedic research community.**
- **We will submit a 5 year follow-up paper to either JBJS Br or Acta Orthopaedica depending on the data outcome and its relevance to the orthopaedic research community. This data will also be presented at orthopaedic conferences such as EFORT, ORS and the National Dutch Orthopaedic Association meeting.**

Authorship

- Number and Order to be agreed by Stryker and Principle investigator (according to requirements of intended Journals)
- If required by the intended Journal, the study will be registered publicly on the required internet site. (Release of information is limited to serve the aforementioned purpose, taking into consideration that scientific methods and protection of intellectual property of the sponsor and the Investigators).

Later publications

- Any publication proposals containing study data (including presentation of the data at any public event) after the general publication has been published in a peer review journal, shall be submitted to Stryker for review and acknowledgement, min. 30 days in advance.

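### The secondary hypothesis of no difference in pain and complications has no margin and no deciding visit, and the planned t-tests and frequency tables cannot support it

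*Combined protocol and SAP*

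**What the plan says.** Section 3 (Objectives) sets the hypothesis: "The secondary hypothesis is that there is no difference in complications and pain during the stair climb and chair raise test", comparing Scorpio NRG PS with Scorpio PS. The next sentence gives its intended meaning: "So more flexion does not result in more anterior knee pain".

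The analysis is in Section 14.1. Its one inferential method is this: "Students T-test will be used to compare variables between groups and various time points". For categorical data it says: "Descriptive statistics will be used like frequency and percent distributions and will be presented in tabular form for categorical variables". Adverse events and complications appear in a list introduced by "There will be summaries and comparisons presented according to", so it is unclear whether complications are to be tested or only tabulated.

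Pain is recorded before surgery (Section 2.1: "a stair climb and chair raise test combined with a VAS (visual analogue scale, appendix 3) score to measure pain") and, under Section 2.3, again with both functional tests at each follow-up. Table 2 in Section 9, in the row "Chair Raise test Stair climb test", and Section 9.1.4 place those tests at 6, 12 and 26 weeks and at 1, 2 and 5 years. Section 6.1 sizes the trial on flexion alone. Section 15 plans a paper on the two-year data ("We plan to submit a two year data paper to either JBJS Br or Acta Orthopaedica") and another at five years.

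Nowhere do the documents give a margin for pain or complications, a deciding visit for pain, or a rule based on a confidence interval.

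**The concern.** A t-test asks whether the data are incompatible with equality. When it is not significant, the designs may be alike or the trial may be too imprecise to tell them apart, and the p-value does not say which. The same holds for similar percentages in a table. The stated hypothesis therefore has no analysis that could confirm it.

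This matters because Section 3 uses the hypothesis to say that the expected gain in flexion is not paid for in pain, and Section 16.1 says that the absence of added risk with the newer design has yet to be proven. Without a margin fixed beforehand, a non-significant result, or a handful of complications in each group, could be reported as no difference while the data still allow a relevant worsening. With two tests, six visits and two planned papers, the choice of which comparison carries the claim is also left open until the results are known.

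**Working it through.** **The plan's own figure.** Section 6.1 gives a 7-degree difference, SD 11, 80% power and two-sided alpha 0.05. The normal approximation is n = 2 × (1.960 + 0.842)² × (11/7)² = 38.8, so 39 per group. The exact t-test solution is 39.7, so 40. Then 80 × 1.10 = 88 in total, or 44 per group. The plan's figure reproduces, but it concerns flexion only.

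**Number of pain comparisons.** 2 tests (Section 2.3) × 6 postoperative visits (Table 2, Section 9.1.4) = 12 between groups.

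**Inputs for pain.** 40 analysed per group is the Section 6.1 figure after loss to follow-up. The documents give no VAS SD and no important VAS difference. SDs of 1.5 to 3, a 1-point benchmark and approximate normality on a bounded 0–10 scale are therefore assumptions.

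- Half-width of the 95% CI: t(0.975, 78) × √(2/40) = 1.991 × 0.2236 = 0.445 SD.
- Chance that a two-sided t-test misses a true 1-point difference: noncentral t on 78 df, with noncentrality 1/(SD × 0.2236).
- Chance of showing not more pain in both tests when the designs are truly equal: both upper 95% limits below an assumed 1-point margin. This was simulated with 1,000,000 trials for each assumed between-test correlation, 0.5 and 0.9, without baseline adjustment.

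| Assumed SD | CI half-width (points) | Power for 1 point | Missed | Both tests below 1-point margin (correlation 0.5 / 0.9) |
|---|---|---|---|---|
| 1.5 | 0.67 | 83.8% | 16% | 73.9% / 79.3% |
| 2 | 0.89 | 59.8% | 40% | 43.6% / 52.8% |
| 2.5 | 1.11 | 42.4% | 58% | 25.8% / 35.2% |
| 3 | 1.34 | 31.3% | 69% | 16.6% / 24.8% |

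**Effect of adjusting for pre-operative VAS.** The residual SD is SD × √(1 − r²). At an assumed correlation r = 0.5 between baseline and outcome, the half-width falls to 0.445 × √0.75 = 0.386 SD. The last column rises to 36.5% / 45.9% at SD 2.5 and to 23.6% / 32.7% at SD 3.

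**Complications.** The documents give no expected rate, so 10% v 20% is assumed. Exact enumeration gives these powers:

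- 40 per group: 16.2% (Fisher), 24.7% (t-test on 0/1 data).
- 44 per group, if every randomised patient contributes: about 17% and 27%.

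Identical results of 4/40 v 4/40 still leave an exact unconditional 95% CI for the risk difference of about ±15.5 percentage points.

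**The case against.** The strongest reply is that this is a secondary hypothesis in a trial sized on flexion. Section 3 states an expectation rather than a finding, and readers could derive intervals from the means, SDs and counts that Section 14.1 promises. Much of this stands. The primary comparison is untouched, and intervals could indeed be derived. What cannot be recovered afterwards is a margin or a deciding visit chosen before the results were known.

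Four stronger readings are tempting but not supported:

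- *The sponsor plans to treat p > 0.05 as proof of no difference.* No section says so. The plan leaves room for that misuse but does not prescribe it.
- *The trial is too small to answer the pain question.* That depends on an SD and a margin the documents do not give. At SD 1.5 a 1-point margin is nearly adequately powered, and a wider justified margin would help at larger SDs.
- *The claim may be tested only if the margin is large enough for good power, around 0.7 SD.* At 40 per group, 80% joint power needs about 0.67 to 0.71 SD. That describes power and is not a condition of validity. A margin fixed in advance controls false claims whatever the power, and low power only makes the result inconclusive.
- *Complications will be t-tested, or will not be tested at all.* Section 14.1 allows either reading, so both were calculated.

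It is also fair to say that every pain and complication figure above rests on assumptions. They show a range, not a prediction.

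**Conclusion.** The concern holds as a mismatch between hypothesis and analysis. Section 3 poses a hypothesis of no difference, and nothing in Section 14.1 could establish it: there is no margin, no deciding visit among 12 pain comparisons, and no confidence-interval rule.

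For pain, the consequence ranges from modest to serious with the unknown SD. Across assumed SDs of 1.5 to 3, between about one in six and about two in three true 1-point worsenings would pass as non-significant. For complications, power stays below 30% for the assumed doubling, whichever test and whichever of the two group sizes is used. The lack of a margin, a visit and a rule is certain from the text; the size of the effect is conditional on the stated assumptions. It should be corrected, but it does not threaten the flexion result.

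**What to change.** **Pain.**

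- Restate the hypothesis openly as one-sided: not more pain with Scorpio NRG PS. This narrows the two-sided wording of Section 3 to what its following sentence is about, and the protocol should say so. A two-sided equivalence claim would be harder to meet.
- For each functional test, report the mean VAS difference (NRG PS minus PS) with a 95% CI at one visit named in advance, adjusted for the pre-operative VAS. Two or five years would each match a planned paper.
- Claim not more pain only if the upper limit is below the margin in both tests. Because both must succeed, no multiplicity correction is needed.
- Justify and fix the margin before any data are seen by group. If none can be justified, label the hypothesis exploratory and make no claim of no difference.
- Report the other visits descriptively. Do not make testing conditional on a minimum margin in SD units.

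**Complications.** Report the risk difference with an exact 95% CI and make no claim of no difference.

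**Cost.** Some protocol wording and a little analysis, with no added patients, visits or data. The real downside is that pain may be reported as inconclusive. Even with equal designs, an assumed 1-point margin would be met in both tests only as often as the last column of the table shows, and somewhat more often with baseline adjustment.

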1 INTRODUCTION

The Scorpio TKA family offers a complete range of Fixed Bearing, Mobile Bearing and revision components, all of which share a single design philosophy. Central to this philosophy is one idea incorporating a single M/L and A/P axis design, supported by a single instrument platform. In an otherwise satisfactory total knee arthroplasty (TKA) (well aligned, well fixed, stable, and with good flexion), symptoms related to extensor mechanism function and the patellofemoral articulation, including anterior knee pain, are the prevalent issues after TKA^{1,3,13}. Many factors influence the outcome of TKA, including prosthetic design. Classic kinematics theory teaches that knee flexion and extension occurs around changing instant centers of rotation. Several reports indicate that TKA's with a multiradius sagittal profile do not restore extensor mechanism moment arms to normal, with the greatest reduction occurring in the last 30 degrees of extension^{5,9}. The validity of the anatomic observations that are the foundation for the changing instant centers of rotation has been challenged.¹¹ Other anatomic studies⁴ indicate that knee motion occurs around a single, fixed flexion-extension axis located in the posterior condyles. This single flexion extension axis is approximated by the transepicondylar axis.² The relatively anterior axis of rotation in multiradius TKA's may account, at least in part, for why extensor mechanism moment arms are shorter after TKA. All other factors being equal, a relatively posterior flexion-extension axis would lengthen the extensor mechanism moment arms and improve extensor mechanism function. Several studies have proved the functional benefit from this improved moment arm. The Scorpio NRG has a redesigned tibial insert, and improved Post and Cam design. Also the posterior condyle height of the femoral component is reduced. These improvements should reduce the operation time, decrease the post operative ventral knee pain, improve rotation in deep flexion and increase maximum flexion. The Standard procedure at the academic hospital Maastricht consists of implantation of the Scorpio PS knee prosthesis, the same prosthesis that will be used in the control group of this study. If a patient's anatomy or specific lifestyle functions require a non scorpio prosthesis, it is possible to implant a NEXgen total knee prosthesis. This category of patients will not be asked to participate in this study.

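### Section 3 infers from equal pain in the two arms that more flexion does not cause anterior knee pain; the planned comparison supports a statement about the prostheses only

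*Combined protocol and SAP*

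**What the plan says.** Section 3 (Objectives) gives the primary hypothesis: "Our primary hypothesis is that the Scorpio NRG PS knee prosthesis has an average flexion of at least 7 degrees higher" than the Scorpio PS. It continues: "The secondary hypothesis is that there is no difference in complications and pain during the stair climb and chair raise test" between the two prostheses, and then draws a corollary: "So more flexion does not result in more anterior knee pain".

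Section 14.1 plans descriptive statistics and one test: "Students T-test will be used to compare variables between groups and various time points". Nothing there relates a patient's flexion to that patient's pain. For another variable the protocol does treat a relation as a question of its own; Section 3 states that "the relation between patella tilting and post-operative pain will be evaluated".

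Section 1 describes what separates the arms: "The Scorpio NRG has a redesigned tibial insert, and improved Post and Cam design", together with a lower posterior condyle. Of these changes it says: "These improvements should reduce the operation time, decrease the post operative ventral knee pain, improve rotation in deep flexion and increase maximum flexion".

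Section 6.1 sizes the trial on "a difference in flexion of 7 degrees, a standard deviation of 11", with 40 patients per group.

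**The concern.** The word that opens the corollary makes it an inference from a comparison of prostheses to a statement about flexion. Randomisation supports a statement about the effect of receiving one prosthesis rather than the other. It would carry over to flexion only if flexion truly differed between the arms and if the design affected pain through flexion alone. The first condition is the hypothesis under test. The second conflicts with Section 1, which lists lower ventral knee pain as an expected effect of the redesign alongside higher flexion.

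At stake is what equal pain would be taken to mean. It could arise because flexion is harmless, because a harmful effect was offset, because little flexion was gained, or because the contrast was too small to show. The plan has no means of telling these apart. Section 15 foresees two-year and five-year papers, to which the sentence could be carried over.

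**Working it through.** **Inputs.** From Section 6.1: difference 7 degrees, SD 11, two-sided alpha 0.05, power 80%, 40 per group, total 88 after 10% loss. The documents give no SD for the VAS and no flexion-pain slope. Assumed here: VAS SD 1.5, 2 or 2.5 on the 0 to 10 scale, and pain rising by 0.5 points per 10 degrees (0.8 as a second value). Power is from the noncentral t distribution with 78 degrees of freedom.

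**1. The plan's own figure.** n per arm = 2 × (1.960 + 0.842)² × (11/7)² = 38.8, so 39 by the normal approximation. By the t-test, power is 79.2% at 39 and 80.3% at 40, so 40 is reproduced. The total is 80 × 1.10 = 88.

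**2. Is the premise of more flexion shown?** The standard error of the flexion difference is 11 × √(2/40) = 2.46 degrees. The noncentrality is the true gain divided by 2.46.

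| True gain (degrees) | Noncentrality | Chance of no significant difference |
|---|---|---|
| 7 | 2.85 | 20% |
| 5 | 2.03 | 48% |
| 3 | 1.22 | 77% |
| 0 | 0 | 95% |

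A non-significant result does not prove that the gain is absent, but it leaves the premise of the corollary unestablished. If the true gain is zero, the arm comparison of pain holds no information on flexion.

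**3. How much pain contrast does a 7-degree gain produce?** If flexion is the only route to pain, the arm difference is slope × 7/10. For a slope of 0.5 this is 0.35 points; for 0.8 it is 0.56 points. The standard error is SD × √(2/40).

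| VAS SD (assumed) | Standard error | Power at 0.35 points | Power at 0.56 points |
|---|---|---|---|
| 1.5 | 0.335 | 17.8% | 38% |
| 2.0 | 0.447 | 12.1% | 24% |
| 2.5 | 0.559 | 9.5% | 17% |

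A version without VAS units gives the same picture. For a within-arm correlation r between flexion and pain, the arm difference is r × 7/11 SD. At r = 0.2, 0.3 and 0.5 that is 0.13, 0.19 and 0.32 SD, with power 9%, 13% and 29%. The trial reaches 80% power only for a pain difference of about (1.960 + 0.842) × √(2/40) = 0.63 SD.

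**4. Offset by the design.** Write the arm difference in pain as (slope × gain/10) + d, where d is any effect of the design on pain that does not pass through flexion. With slope 0.5, gain 7 and d = −0.35, the sum is 0.35 − 0.35 = 0: the arms have equal pain although flexion is harmful. Section 1 gives reason to expect a negative d, if ventral pain there means the anterior pain of Section 3. A larger sample or an equivalence margin would bound the sum more tightly but would not separate its two parts.

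**The case against.** The strongest reply is that the sentence is a gloss on a hypothesis in the Objectives. It is neither a result nor a decision rule, and neither Section 14.1 nor Section 15 says that such a conclusion will be drawn. This stands. A reader might infer that the trial is set to report that flexion is harmless whatever happens to flexion. The documents do not say so. In context, more flexion most naturally means the extra flexion expected with the NRG, so the gloss presupposes the primary hypothesis.

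A second reply is that the arm comparison is weak rather than uninformative, since step 3 gives it some power. This also stands as far as it goes: low power alone would not justify saying that the comparison cannot address flexion. What justifies it is the offset in step 4, which rests on Section 1.

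A third reply is that the preceding sentence of Section 3 already makes the prosthesis-level statement. That is largely so, and it is why the correction is small.

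A reader might also infer that regressing pain on flexion in the same 80 patients would settle the matter with good power. The documents do not support that. Without adjustment, the standard error of the slope per 10 degrees is 10 × SD/(11 × √79), or 0.153 to 0.256 for SD 1.5 to 2.5. By the normal approximation, power at a slope of 0.5 then runs from about 90% down to 50%, purely on an assumed SD. Adjusting for arm and pre-operative flexion would lower it. Pain may also limit measured flexion, which could mask or reverse a harmful effect in a same-visit slope. Such a model shows an association, and no claim about its power should be made.

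**Conclusion.** The concern holds as a matter of interpretation. Equal activity pain in the two arms would not support the statement that more flexion does not result in more anterior knee pain, because the t-tests compare prostheses that Section 1 expects to differ in pain for reasons besides flexion.

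Two further points add to this. The flexion gain may not be shown (20% of the time at a true 7 degrees, 48% at 5; these use only Section 6.1 figures). And a true 7-degree gain with an assumed slope of 0.5 points per 10 degrees moves the arm difference by only 0.35 points, detected about 10 to 18% of the time for an assumed VAS SD of 2.5 to 1.5.

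The weight is low. The primary endpoint, the sample size and the comparison of complications are unaffected. Only the reading of one secondary hypothesis changes.

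**What to change.** In Section 3, replace the corollary with a statement at the level of the prostheses: the Scorpio NRG PS does not give more pain during stair climb and chair raise than the Scorpio PS. Add that no conclusion about flexion itself will be drawn from the arm comparison. Whether a non-significant t-test is enough to support even the prosthesis-level statement is a separate question; a margin would help there but would not repair the step to flexion.

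Optionally, add to Section 14.1 an exploratory regression of VAS pain on flexion at the same visit, adjusted for arm, pre-operative VAS and pre-operative flexion. Report the slope per 10 degrees with its 95% confidence interval, labelled as an association that may be affected by pain limiting flexion.

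The cost is one sentence and, if wanted, one model. Table 2 and Section 9.1 already schedule the clinical examination and the functional tests together, before surgery and at each follow-up from 6 weeks, so no new data are needed. The trial gives up a statement about flexion and pain that its design cannot support.
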